3.3 Secondary objectives

- 3.3.1** To characterize the safety profile of $^{177}\text{Lu-DOTA}^0\text{-Tyr}^3\text{-Octreotate}$ in combination with nivolumab. [Applicable to both phase 1 and 2 portions]
- 3.3.2** In patients who were not progressing before initiating combo therapy: [Applicable to the phase 2 portion]
- To assess DCR and ORR after treatment with $^{177}\text{Lu-DOTA}^0\text{-Tyr}^3\text{-Octreotate}$ plus nivolumab.
 - To assess OS
 - To assess whether the metabolic response seen on a NETSPOT[®] PET scan obtained on cycle 2 day 1 will predict response to study treatment.

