5.1.2 Phase II

The phase II portion will consist of patients with ES-SCLC who completed platinum based standard first-line chemotherapy (e.g. 4-6 cycles of platinum plus etoposide or irinotecan) without disease progression (responders plus stable disease) at the time of initiation of the combination therapy with $^{177}\text{Lu-DOTA}^0\text{-Tyr}^3\text{-Octreotate}$ and nivolumab. Eligible patients will then be randomly allocated in two arms: one will be treated with the combination of $^{177}\text{Lu-DOTA}^0\text{-Tyr}^3\text{-}$

Octreotate and nivolumab, and the other arm will continue be followed (observation) after completion the standard chemotherapy treatment.

Randomization:

Patients who do not receive radiotherapy after chemotherapy

- The randomization must occur within 6 weeks of the last chemotherapy cycle.
- The study treatment must start within 2 weeks from randomization, but no less than 2 weeks from last dose of chemotherapy.

Patients who receive radiotherapy (including prophylactic cranial radiation and/or thoracic radiation) after chemotherapy

- Randomization must occur at least 8 weeks after completion of radiation therapy but within 12 weeks after completion of radiation therapy.

Randomization process:

- OnCore will be used as statistical center and the randomization algorithm will be developed by the study biostatistician.
- The project management department will be the first point of contact for assessment through email.

Courses are defined as 56 days of dosing. Nivolumab will be given until progressive disease, patient withdrawal, or toxicities. For patients randomized to the observation group, cross-over at the time of disease progression will be allowed, since the primary endpoint is PFS and not OS.

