11.2 Sample Size and Accrual

ES-SCLC (i.e. SCLC that has spread beyond the supraclavicular areas or with distant metastases) remains incurable with current management options, and patients are treated with combination chemotherapy. Several chemotherapy combinations are active in SCLC, but usually a platinum-containing regimen is chosen. The ORR of platinum-based therapy administered to patients with ES-SCLC ranges from 40 to 80%, and the median PFS ranges from 5 to 7 months in patient series treated in a clinical trial setting (phase-II/III studies) [9, 10, 48-55]. A placebo-controlled randomized phase II study of maintenance sunitinib shows that median PFS was 2.1 months in the placebo group[56].

Based on historic average clinical outcomes, we propose a clinical study that will be integrated by a dose finding approach followed by a randomized phase II study with PFS as the primary endpoint, designed to have 80% power for a two-sided 0.05 level test. The completion of the first part of the study will require approximately 8-9 months for accrual assuming 9 to 12 patients will be required for the completion of the phase I portion with the participation of 7 institutions (Georgetown Lombardi comprehensive Cancer Center, Memorial Sloan Kettering Cancer Center, University of California, Los Angeles, University of California, San Francisco, Vanderbilt University, Hackensack University Medical Center, and Walter Reed National Military Medical Center).

For the phase II portion, assuming a median PFS of 2 months following completion of first-line therapy with a platinum-based chemotherapy for ES-SCLC in the control arm, and an expected median PFS of 5 months for the maintenance therapy with $^{177}\text{Lu-DOTA}^0\text{-Tyr}^3\text{-Octreotate}$ and nivolumab in the experimental arm (hazard ratio 0.4), it will be required to document 40 PFS events from a total population of 44 patients enrolled during a period of 18 month, including a minimum follow up of 10 months, with an expected accrual rate of 3-4 patients per month and the participation of 6-7 institutions. Assuming a potential 15% dropout, the total number of patients to recruit will be 52 [57-59].

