11.3 Data Analyses Plans

PFS will be defined as the time from random assignment to disease progression or death from any cause, whichever comes first. OS will be defined as the time from random assignment to death from any cause; living patients will be censored at the date of last follow-up. Survival will be estimated and plotted by the Kaplan–Meier method. In addition, the median progression-free and overall survival times will be reported along with the 95% confidence intervals. The cox proportional hazards regression model will be used to obtain hazard ratios (HRs) and the log-rank test will be utilized to compare survival estimates between the maintenance group and the control observation group. Secondary endpoints will be analyzed when the required number of events for the primary endpoint (PFS) has been met. The DCR is defined as the proportion of patients with a best overall response of CR, PR, or SD. The ORR is defined as the proportion of patients with a best overall response of CR or PR. All randomized subjects will consist of the safety population. This population will be used for all summaries of safety data (AEs, concomitant medications, laboratory data). P-values less than 0.05 will be considered significant. All statistical analyses will be performed using SAS (Version 9.4; SAS Institute, Cary, NC). [name] will serve as the study statistician.

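### Section 11.3 lets any p-value below 0.05 count as significant, so OS could be declared significant after a negative PFS result

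*Combined protocol and SAP*

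**What the plan says.** Section 11.2 gives the phase II part one primary endpoint, PFS, and one design test, "designed to have 80% power for a two-sided 0.05 level test". The target is 40 PFS events.

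Section 11.3 defines both PFS and OS, says that medians of both will be reported with confidence intervals, and then says that "the log-rank test will be utilized to compare survival estimates between the maintenance group and the control observation group". The phrase is not limited to PFS, so its natural reading covers OS too. On timing, "Secondary endpoints will be analyzed when the required number of events for the primary endpoint (PFS) has been met". The significance rule for the whole section is "P-values less than 0.05 will be considered significant".

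The secondary efficacy objectives in section 3.3 are OS, the response rates ("To assess DCR and ORR after treatment with" the combination) and a PET question: "To assess whether the metabolic response seen on a NETSPOT" scan at cycle 2 day 1 predicts response. Section 11.3 defines ORR and DCR as proportions. It names no between-arm test for them and no test for the PET objective.

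Sections 3.3 and 11.1 to 11.3 contain no testing order, no division of alpha, and no statement that the secondary results are descriptive.

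**The concern.** The 0.05 in section 11.2 is a design level for one test. The 0.05 in section 11.3 is a reporting rule for every p-value. The secondary analyses are triggered by an event count, which will be reached whether PFS succeeds or fails. Nothing in the text stops a report that PFS was not significant but OS was, with both judged at full alpha.

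OS is the result most exposed to this. Section 5.1.2 allows cross-over at progression "since the primary endpoint is PFS and not OS", so the sponsor already accepts that OS is not what the trial was designed to answer. Yet 11.3 gives an OS p-value, taken at a cutoff set by PFS events in about 52 patients, the same standing as the primary result. A reader of the final report could not tell a controlled claim from an uncontrolled one.

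**Working it through.** **Inputs.** From the documents: two-sided alpha 0.05 and 80% power, hazard ratio 0.4, 40 events, 44 patients raised to 52 for 15% dropout (section 11.2); log-rank comparison of survival and the 0.05 rule (section 11.3). Assumed, because the documents do not give them: 1:1 allocation, and a correlation between the PFS and OS test statistics of 0.5, with a range of 0 to 0.8.

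**Step 1: what the stated 0.05 pays for.** The plan gives no familywise error figure, so the figure to reproduce is the event count. By Schoenfeld's formula,

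events = 4(1.960 + 0.842)² / (ln 0.4)² = 4 × 7.85 / 0.840 = 37.4, so 38.

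Freedman's formula gives 43. The planned 40 lies between them, with power of 82.6% and 77.4% respectively. A one-sided 0.05 test would need only 30 or 34. The dropout step is 44 / 0.85 = 51.8, so 52. The design therefore uses the full two-sided 0.05 on PFS and leaves nothing for a second test.

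**Step 2: two tests, both nulls true, either direction.**

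- If independent: 1 − 0.95² = 0.0975.
- If correlated: 1 − P(|Z₁| < 1.96 and |Z₂| < 1.96) from the bivariate normal.

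| Correlation | Any false significant result | False result in favour of treatment |
|---|---|---|
| 0 | 9.8% | 4.9% |
| 0.3 | 9.5% | 4.8% |
| 0.5 | 9.1% | 4.5% |
| 0.7 | 8.4% | 4.2% |
| 0.8 | 7.8% | 3.9% |
| PFS alone | 5.0% | 2.5% |

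The last column uses 0.025 per test; at independence it is 1 − 0.975² = 0.0494. At correlation 0.5, either column is about 1.8 times its value for PFS alone (9.1/5.0; 4.5/2.5).

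**Step 3: check by simulating the log-rank tests.** Both arms had median PFS of 2 months, 52 patients entered over an assumed 15 months, and data were cut at 40 PFS events. Median survival after progression was assumed to be 3 to 8 months. The PFS and OS statistics had correlation 0.30 to 0.52, with 17 to 27 OS events at the cut. Any two-sided rejection occurred in 9.9% to 10.4% of trials, and any rejection in favour of treatment in 4.8% to 5.4%. These are slightly above step 2 because each small-sample log-rank test had a size of 5.2% to 5.7% rather than 5%.

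**Step 4: the scenario of a negative PFS result.** At correlation 0.5, PFS is not significant but OS is, in either direction, in 9.07% − 5.00% = 4.07% of null trials. Half of these, about 2.0%, favour the treatment. Given a non-significant PFS result, the chance of a false significant OS result is 0.0407 / 0.95 = 4.3%.

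**Step 5: effect of the fix.** If OS is tested only after a significant PFS result, or is never tested formally, any false formal claim under the global null requires a false PFS result first. The chance is then 5.0% in either direction and 2.5% in favour of treatment.

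**The case against.** The strongest reply is that this is a 52-patient randomized phase II trial with one clearly named primary. Section 3.1 states the efficacy hypothesis for PFS only, section 3 separates primary from secondary objectives, section 11.2 powers one test, and the cross-over sentence shows that OS is not the intended claim. Secondary endpoints in such trials are not usually alpha-controlled, and section 11.3 does not say that a secondary result can rescue a failed primary.

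Most of that stands. The PFS test keeps its 0.05 level, and full familywise control here would be a preference. What does not stand is the step from there to no change: if the secondaries are only supportive, the plan should say so, and its one rule on significance says otherwise. Section 6.1 calls the scan comparison before and after chemotherapy exploratory, so the label was available but was not used for the secondary endpoints.

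Three stronger readings are tempting, and the documents do not support them.

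- A reader might count all five endpoints (PFS, OS, ORR, DCR, PET) and arrive at about 18% at correlation 0.5, or 22.6% if independent (1 − 0.95⁵). That needs tests that the plan does not name. ORR and DCR are to be assessed after the combination. The cycle 2 day 1 scan is listed in section 6.2 for patients receiving study treatment and not for those under observation, so that objective is a predictive question within the treated arm and not a comparison of arms.
- A reader might call the 9% the chance of a false efficacy claim. It counts results in both directions; the part in favour of treatment is about half.
- A reader might infer that a failed PFS test makes a false OS result more likely than usual. Step 4 shows 4.3%, slightly below nominal, because the two tests are positively correlated. The problem is the status given to that result, not an unusual error rate for it.

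**Conclusion.** The point holds in a limited form. Section 11.3 contains an actual rule, not merely a gap, under which OS may be called significant at full alpha after a negative primary. For PFS and OS together, the chance of at least one false significant result is about 9.1% in either direction (7.8% to 9.8%), or about 4.5% in favour of treatment (3.9% to 4.9%) against 2.5% for PFS alone.

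These figures assume that both nulls are true and that the statistics are jointly normal with correlation between 0 and 0.8. The log-rank simulation, with assumed accrual and post-progression survival, gives about 10% and 5%. They also rest on reading the log-rank sentence as covering OS. The primary PFS inference, its power and the sample size are unaffected. This is a cheap improvement worth making, not a defect in the design.

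**What to change.** Replace the significance sentence in section 11.3 with wording such as:

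> The log-rank test of PFS at 40 events is the only confirmatory test (two-sided 0.05). OS, ORR, DCR and the PET analysis are reported as estimates with 95% confidence intervals; their p-values are descriptive.

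If the sponsor wants a formal OS claim, use a fixed sequence: test OS at two-sided 0.05 only if PFS is significant, and keep the descriptive label for the rest.

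The cost is one or two sentences, with no added patients and no change to the 40 events. Confidence intervals for median PFS and OS are already planned; those for ORR, DCR and the PET analysis would need to be named. The downside is that a secondary p-value below 0.05 can no longer be called significant by itself.

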12.0 STUDY MANAGEMENT

12.1 Institutional Review Board (IRB) Approval and Consent

It is expected that the IRB will have the proper representation and function in accordance with federally mandated regulations. The IRB should approve the consent form and protocol. In obtaining and documenting informed consent, the investigator should comply with the applicable regulatory requirement(s), and should adhere to Good Clinical Practice (GCP) and to ethical principles that have their origin in the Declaration of Helsinki.

Before recruitment and enrollment onto this study, the patient will be given a full explanation of the study and will be given the opportunity to review the consent form. Each consent form must include all the relevant elements currently required by the FDA Regulations and local or state regulations. Once this essential information has been provided to the patient and the investigator is assured that the patient understands the implications of participating in the study, the patient will be asked to give consent to participate in the study by signing an IRB-approved consent form.

Prior to a patient's participation in the trial, the written informed consent form should be signed and personally dated by the patient and by the person who conducted the informed consent discussion.

12.2 Required Documentation

Before the study can be initiated at any site, the following documentation must be provided to the Research office.

- A copy of the official IRB approval letter for the protocol and informed consent
- IRB membership list
- CVs and medical licensure for the principal investigator and any associate investigators who will be involved in the study
- Form FDA 1572 appropriately filled out and signed with appropriate documentation (NOTE: this is required if UNC holds the IND. Otherwise, the affiliate Investigator's signature on the protocol is sufficient to ensure compliance)
- A copy of the IRB-approved consent form
- CAP and CLIA Laboratory certification numbers and institution lab normal values
- Executed clinical research contract

12.3 Registration Procedures

The study site coordinator or physician is responsible to screen potential subjects using the eligibility criteria, obtain informed consent and HIPAA authorization forms from each consenting subject, and to provide the Eligibility Packet (defined below) to the Quality Assurance Office (QAO) for review. The QAO is responsible to verify eligibility of all subjects screened to investigator initiated or multi-site clinical research trials, to assign subject IDs to each eligible patient, and to inform the study site of the assigned subject ID or any eligibility issues within one business day.

Subjects may not begin treatment until eligibility is confirmed and subject ID is assigned by QAO.

Procedures:

1. Patient signs Informed Consent Form (ICF) and HIPAA authorization form.
 - ICF is administered by site coordinator or treating physician.
2. Site screens subject for eligibility criteria
 - Site coordinator or treating physician completes eligibility checklist
 - If patient does not meet eligibility criteria, stop and report screen failure.
3. Site faxes the eligibility packet to QAO at [contact] or emails the packet to [contact]
 - Eligibility Packet to include:
 - Completed QAO Registration Form
 - Signed and dated Eligibility Checklist, completely filled out
 - Signed and dated ICF
 - Signed and dated HIPAA authorization form
 - All source documents required for verification of eligibility
4. QAO verifies eligibility using Eligibility Packet

- If eligibility is not verified, stop and inform site of eligibility issues or questions
5. If eligibility is verified, QAO does the following:
- Assigns Subject ID
 - Registers the patient in the study and in the CTMS
 - Emails the Subject ID to the study site within one business day of receiving the Eligibility Packet

12.4 Data Management and Monitoring/Auditing

The Georgetown Lombardi Comprehensive Cancer Center (LCCC) will be responsible for the data and safety monitoring of this trial. As this study is an investigator initiated Phase I/II study it is considered a high risk study which requires real-time monitoring by the PI and study team and quarterly reviews by the LCCC Data and Safety Monitoring Committee (DSMC).

The Study Chairs and Associate Investigators will review the data including safety monitoring at their monthly teleconferences of participating sites.

All “reportable” (defined above) Severe Adverse Events (SAEs) are required to be reported to the local and to the Georgetown IRB, as detailed above, and to the chair of the DSMC. Based on SAEs, the IRB retains the authority to suspend further accrual pending more detailed reporting and/or modifications to further reduce risk and maximize the safety of participating patients.

Progress on the trial and the toxicities experienced will be reviewed by the LCCC Data and Safety Monitoring Committee every three months from the time the first patient is enrolled on the study. Results of the DSMC meetings will be forwarded to the IRB with recommendations regarding need for study closure.

DSMC recommendations should be based not only on results for the trial being monitored as well as on data available to the DSMC from other studies. It is the responsibility of the Study Chair to ensure that the DSMC is kept apprised of non-confidential results from related studies that become available. It is the responsibility of the DSMC to determine the extent to which this information is relevant to its decisions related to the specific trial being monitored.

A written copy of the DSMC recommendations will be given to the trial Study Chair and the IRB. If the DSMC recommends a study change for patient safety or efficacy reasons the Study Chair must act to implement the change as expeditiously as possible. In the unlikely event that the Study Chair does not concur with the DSMC recommendations, then the LCCC Associate Director of Clinical Research must be informed of the reason for the disagreement. The Study Chair, DSMC Chair, and the LCCC AD for Clinical Research will be responsible for reaching a mutually acceptable decision about the study and providing details of that decision to the IRB. Confidentiality must be preserved during these discussions. However, in some cases, relevant data may be shared with other selected trial investigators and staff to seek advice to assist in reaching a mutually acceptable decision.

If a recommendation is made to change a trial for reasons other than patient safety or efficacy the DSMC will provide an adequate rationale for its decision. If the DSMC recommends that the trial be closed for any reason, the recommendation will be reviewed by the Associate Director for Clinical Research at GU-LCCC. Authority to close a trial for safety reasons lies with the IRB, with the above described input from DSMC and the AD for Clinical Research.

Of note, the DSMC will also review the safety data of the patients enrolled outside of Georgetown University. The multi-institutional coordinator will be tasked with the job of collecting all primary source documentation for patients enrolled outside of Georgetown University. In addition, the data managers at each site will be entering data into the Georgetown database, so that all data will be available for the DSMC at Georgetown to review. Faxed records should be sent to [name] with an email to the multi-institutional coordinator and [name] to confirm receipt of those records.

12.5 Adherence to the Protocol

Except for an emergency situation in which proper care for the protection, safety, and well-being of the study patient requires alternative treatment, the study shall be conducted exactly as described in the approved protocol.

12.5.1 Emergency Modifications

Investigators may implement a deviation from, or a change of, the protocol to eliminate an immediate hazard(s) to trial subjects without prior IRB approval. For any such emergency modification implemented, an IRB modification form must be completed within five (5) business days of making the change.

12.5.2 Single Patient/Subject Exceptions

Any request to enroll a single subject who does not meet all the eligibility criteria of this study requires the approval of the Principal Investigator and the IRB.

12.5.3 Other Protocol Deviations/Violations

All other planned deviations from the protocol must have prior approval by the Principal Investigator and the IRB. According to the IRB, a protocol deviation is any unplanned variance from an IRB approved protocol that:

- Is generally noted or recognized after it occurs.
- Has no substantive effect on the risks to research participants.
- Has no substantive effect on the scientific integrity of the research plan or the value of the data collected.
- Did not result from willful or knowing misconduct on the part of the investigator(s).

An unplanned protocol variance is considered a violation if the variance:

- Has harmed or increased the risk of harm to one or more research participants.
- Has damaged the scientific integrity of the data collected for the study.
- Results from willful or knowing misconduct on the part of the investigator(s).
- Demonstrates serious or continuing noncompliance with federal regulations, State laws, or University policies.

If a deviation or violation occurs without prior approval from the Principal Investigator, please follow the guidelines below:

Protocol Deviations: Personnel will report to any sponsor or data and safety monitoring committee in accordance with their policies. Deviations should be summarized and reported to the IRB at the time of continuing review.

Protocol Violations: Violations should be reported by study personnel within one (1) week of the investigator becoming aware of the event using the same IRB online mechanism used to report Unanticipated Problems.

